2.2 Secondary Objectives

- To determine if Caucasian men and men of African-American descent with and without prostate cancer have different proteomic profiles.
- To assess reproducibility of proteomic profiles over different runs, platforms, and sites.
- To procure a DNA repository from these patients undergoing prostate biopsy for future assessment of kallikrein gene expression.
- To establish a bank of DNA, serum, and frozen lymphoblastoid cells from these patients for the purpose of enabling genetic investigations in men with a diagnosis of prostate cancer.

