MALDI-TOF MS-based Standard Profiling (S): 500 samples from men undergoing prostate biopsy (estimated 150 malignant; 350 benign) will be analyzed. The number of MALDI-based analyses will be as follows: 500 samples x 3 independent analyses over

IRB
PB

Amended: 2/1/12

Memorial Sloan-Kettering Cancer Center IRB Protocol

IRB#: 08-114 A(4)

time = 1500 MALDI-analyses per site; 3000 analyses for both sites combined. Feature selection and class prediction will be performed on the data generated from these samples. Additionally, reproducibility will be checked.

MALDI-TOF MS-based Quantitative Profiling (Q): A random selection of 200 serum samples (100 malignant; 100 benign) will be analyzed at two time points at both *NY consortium* sites. These 200 samples will be the same samples examined by the remaining technologies. The number of analysis will therefore be: $200 \times 2 = 400$ per site; 800 for both sites combined. Statistical and reproducibility analysis will be same as described above

MALDI-TOF MS-based Protease Assays (A): A random selection of 200 serum samples (100 malignant; 100 benign) will be analyzed at two time points at both *NY consortium* sites. These will be the same as the “Q” samples above. The number of analysis will therefore be: $200 \times 2 = 400$ per site; 800 for both sites combined. Statistical and reproducibility analysis will be same as described above

LC-MS Ion Intensity-based Standard Profiling (S): The NYU site will use the optimized LC-MS protocol to analyze sera from 100 patients with prostate cancer on biopsy and sera from 100 patients with a benign prostate biopsy. These will be the same as the “Q” samples above. Both the NYU and MSKCC will analyze each sample, and all analyses will be repeated 3 months later for a total of $(100 + 100) \times 2 = 400$ analyses performed at each site. All statistical analyses, including classification and comparison of repeat analyses at each site as well as results between sites, will be performed.

LC-MS Ion Intensity-based Quantitative Profiling (Q): A random selection of 100 malignant and 100 benign serum samples will be analyzed for a total of 200 LC-MS runs at both sites. These will be the same as the “Q” samples above. Evaluation of whether inclusion of the labeled standard peptides improves the sensitivity and specificity of the analyses will be performed.

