11.0 BIOSTATISTICS

This is a prospective, serum proteomics study of men who are to undergo prostate biopsy. The purpose is to determine if proteomic profiles can be used to distinguish between men with prostate cancer on biopsy from men with no cancer on biopsy. Overall, 500 men will be part of the study. Based on previous experience, about 30% (150 patients) will have cancer and about 70% (350 patients) will not. Accrual is expected to take two years.

An initial biopsy will be undertaken for these patients because of a suspicion of prostate cancer. Because there is about a 20% false negative rate on a single biopsy, and a negligible false positive rate, a second biopsy will be recommended at six months only for those who are negative on the first biopsy. Patients who are positive on the first or second biopsy will be assigned to the “cancer” group, while those who are negative for all their biopsies will be assigned to the “no cancer” group. Assuming the two biopsies can be treated as independent, there would be about 4% that should be in the “cancer” group that would be assigned to the “no cancer” group if all those negative on the first biopsy got the second biopsy. We believe that over 90% of the patients that are negative on the first biopsy will get the second biopsy, leading to an expected false negative rate of 5 to 6%. Since the number incorrectly assigned should be small, we ignore it in the calculations below.

The data from each proteomic study is a two-dimensional plot of mass over charge (m/z) and intensity. The intensity at a particular m/z is proportional to the amount of the peptide with that particular molecular weight in the sample. The m/z values are continuous, but as a first step, these values will be reduced to a finite set of “bins” based on intensity “peaks” across samples, as previously described.¹² To prevent against bias, the bins and the intensities at each bin will be computed while blinded to disease status. The value for each m/z bin for each

**IRB
PB**

Amended: 2/1/12

Memorial Sloan-Kettering Cancer Center IRB Protocol

IRB#: 08-114 A(4)

sample will be analyzed in two ways. One way will be to use the actual intensity measure, while the other way will be to convert it to a binary (absence or presence) value.

Primary Objectives:

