Prediction models for “cancer” or “no cancer” membership will be developed. The first 250 patients accrued will be used as a training set and the second 250 will be used as a validation set. As the optimal analysis methods for these types of experiments are undefined, at least three approaches will be evaluated. One simple approach that will be used is to build a score for each patient based on forward stepwise logistic regression. The second method that will be used involves a statistical technique called “boosting” that puts extra emphasis on correct assignment of difficult cases. This approach was shown to be useful in the analysis of proteomic data in an earlier study.¹⁶ This will be combined with a logistic regression approach. A third technique that will be used is called “logic regression”.¹⁷ Here, a search is made through a large subset of the many possible combinations of binary predictors (in this case bins) to build a good prediction rule. This will be straightforward when the data is binary, but it can be utilized for continuous data by setting optimal thresholds for the intensities. In Aim 2, proteomic data will be combined with known biomarkers (PSA and hK2) and compared to models with just the biomarkers. Therefore, for this analysis, the known biomarkers will be forced into models; for Aim 1, only proteomic data will be included. To prevent over-fitting of the training set, 10-fold cross-validation will be utilized in the modeling. The modeling results will be evaluated using the area under the ROC curve (AUC), and the best models will be validated on the validation set. Models will be constructed both with and without clinical variables such as age and family history.

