The proteomic profiles of Caucasian men and of African-American men will be compared to see if the same peaks that are predictive in one are predictive in the other. In addition, the AUCs for the two groups will be compared based on models that use all the data.²⁰ Finally, separate models will be built for the two groups and the AUCs will again be compared.

As mentioned in section 4, we distinguish two aspects of reproducibility: *analytical* reproducibility, that is, whether a proteomics machine produces similar peaks on repeated samples, and *inferential* reproducibility, whether a proteomics experiment produces similar conclusions when repeated.

The basic method for assessing analytic reproducibility will be through the concordance correlation coefficient (CCC)²¹ of the intensity estimates. This CCC is a measure of the agreement between two readings of the same sample via the variation from the 45 degree line through the origin. It is on the same -1 to 1 scale as the standard Pearson correlation. Since there are about 600 bins per sample, there will be 600 CCCs for every comparison. Therefore, we will compute summary statistics of the CCCs. These summaries will be based on all the bins and just the discriminating bins. Since the statistic is only pair-wise, different analyses will have to be done for the three time points, the two sites, and the two platforms (MALDI and LC-MS). The only comparison between the platforms will be between standard MALDI and standard LC-MS.

Inferential reproducibility will consist of two components: determination of whether the same peaks are discriminating and comparisons of the AUCs for the prediction of cancer or no cancer. These comparisons will be made for the same varying conditions as for analytic reproducibility. For the former, discriminating peaks will be identified using a variety of thresholds and the differences will be reported as summary statistics. For the latter, formal testing of differences in AUCs will be undertaken, as well as summary statistics. A question of particular interest will be whether the difference in the estimated AUC from the two sites using the standard MALDI platform is statistically significant.

IRB
PB

Amended: 2/1/12

Memorial Sloan-Kettering Cancer Center IRB Protocol

IRB#: 08-114 A(4)

The last two secondary aims involve collection of material for future studies and no current data analyses.

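### For the AUC part of between-laboratory reproducibility, the only formal tool is a test of no difference, with no confidence interval or margin, so a non-significant result could be misread as agreement.

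*Combined protocol and SAP*

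**What the plan says.** Section 2.2 lists as a secondary objective: "To assess reproducibility of proteomic profiles over different runs, platforms, and sites". Here the sites are the two mass-spectrometry laboratories (MSKCC and NYU), not the recruiting hospitals. For standard MALDI profiling, Section 4.2 runs all 500 samples three times at each laboratory, "1500 MALDI-analyses per site; 3000 analyses for both sites combined", so the readings are paired by patient.

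Section 11.0 (Secondary Objectives) separates two kinds of reproducibility.

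- Analytical: "The basic method for assessing analytic reproducibility will be through the concordance correlation coefficient (CCC", computed bin by bin, then summarised over all bins and over the discriminating bins.
- Inferential, meaning whether a repeated experiment leads to similar conclusions: "determination of whether the same peaks are discriminating and comparisons of the AUCs for the prediction of cancer or no cancer".

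Peak overlap is to be reported as summary statistics at several thresholds. For the AUCs, "formal testing of differences in AUCs will be undertaken, as well as summary statistics". The between-laboratory question picked out is "whether the difference in the estimated AUC from the two sites using the standard MALDI platform is statistically significant".

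For this comparison the section gives no margin, confidence interval, power statement or rule for reading a non-significant result. The CCC and peak-overlap summaries have no acceptance limit either.

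**The concern.** The objective asks about similarity, while the formal tool tests for difference. The two can part in both directions. If the laboratories' scores are only loosely correlated, which is itself a form of poor reproducibility, the paired difference is imprecise and a real loss of accuracy is likely to be non-significant. If the scores are very highly correlated, a difference too small to matter can be significant.

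The other planned evidence does not settle the matter. CCCs describe agreement of intensities and peak overlap describes agreement of peak lists; neither measures diagnostic accuracy. The AUC summary statistics would help, but their content is not specified.

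At stake is whether the report can fairly say that the diagnostic performance of a serum profile carries over to a second laboratory. The gain that Aim 1 is sized to detect is 0.86 − 0.80 = 0.06, so a loss of 0.05 at the second laboratory would remove most of it.

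**Working it through.** **Inputs from the documents.** Validation set of 250 (Section 11.0: "The first 250 patients accrued will be used as a training set and the second 250 will be used as a validation set"). Cancer fraction: "about 30% (150 patients) will have cancer and about 70% (350 patients) will not", so 0.30 × 250 = 75 with cancer and 175 without. AUCs of 0.86 and 0.80 come from the Aim 1 sample-size statement, with type I error 0.05.

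**Assumptions.** The between-laboratory correlation is not given; Section 11.0 calls the analogous Aim 2 correlation unknown. I use 0.5 to 0.9. The 0.05 loss, the starting AUC of 0.86 (a detectable value in the plan, not an expected one), the two-sided 5% test and a single run per laboratory are also assumptions.

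**Step 1: reproduce the plan's own figures.** The plan gives none for the laboratory comparison, so I checked the variance formula on Aims 1 and 2. For an equal-variance binormal score with m cases and n controls,

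Var(A) = [A(1 − A) + (m + n − 2)(Q − A²)] / (mn),

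where Q is the bivariate normal probability at (z_A, z_A) with correlation 0.5.

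- A = 0.86: Q = 0.7723, Var = [0.1204 + 248 × 0.0327] / 13,125, SE = 0.0250.
- A = 0.80: SE = 0.0301. A = 0.89: SE = 0.0219.
- Aim 1, one-sided: Φ(0.06/0.0250 − 1.645) = 77%; 80% power is reached at AUC 0.862.
- Aim 2, one-sided: Φ(0.09/√(0.0301² + 0.0219²) − 1.645) = 78%; 80% power is reached at 0.8925.

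These match the stated 0.86 and 0.89 to two decimals if the tests are one-sided. Two-sided, power would be about 67% and 68%.

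**Step 2: between-laboratory test by formula.** For A = 0.81, SE = 0.0293. With r the correlation of the two AUC estimates, SE(d) = √(v₁ + v₂ − 2r√(v₁v₂)). At r = 0.7, SE(d) = 0.0214 and power = Φ(0.05/0.0214 − 1.96) = 65%, so 35% of such losses are missed. At r = 0.5, 0.8 and 0.9 the missed share is 55%, 19% and 3%.

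**Step 3: simulation.** Paired binormal scores were simulated for the same men at both laboratories, with the DeLong variance of the paired difference. The correlation here is between scores; score correlations of 0.5 to 0.9 give AUC correlations of about 0.45 to 0.86, which is why the missed shares are somewhat higher than in step 2. Repeat simulations differ by up to about 3 percentage points.

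| Score correlation | 0.86 to 0.81 missed, 75/175 | 95% CI half-width, 75/175 | Missed, all 150/350 | Agreement within ±0.05 shown, equal laboratories, 75/175 |
|---|---|---|---|---|
| 0.5 | 59% | 0.057 | 31% | 19% |
| 0.7 | 42% | 0.046 | 11% | 53% |
| 0.8 | 27% | 0.038 | 4% | 77% |
| 0.9 | 4% | 0.029 | under 1% | 97% |

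The last column sets both laboratories at 0.86 and requires the 90% CI to lie inside an illustrative margin of ±0.05.

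**Step 4: the opposite error.** With 150/350 and a correlation of 0.9, a true difference of only 0.02 is significant about 56% of the time.

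**Step 5: platforms.** Section 11.0 gives LC-MS a test set of 50 cancers and 50 benign. There a 0.05 loss is missed about 78%, 71%, 58% and 36% of the time at the four correlations. With equal platforms, agreement within ±0.05 would be shown only about 0.5%, 7%, 23% and 67% of the time.

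**The case against.** A reader might infer that the plan judges reproducibility by significance, so that a loss of accuracy passes as reproducible and noisier data pass more easily. The documents do not support that. Section 2.2 sets out to assess reproducibility, not to declare it, and Section 11.0 contains no pass/fail rule and nowhere equates a non-significant test with agreement. It also plans peak overlap as the other half of inferential reproducibility, CCCs on the discriminating bins, and summary statistics for the AUCs. That part of the objection stands, and it limits the point to the AUC component and to a risk of misreading.

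The size is also uncertain. The correlation drives it, and the design has features meant to raise agreement: the same sera, a mirrored robot/MALDI platform, common bins and three runs per sample. Section 11.0 does not say that the between-laboratory test is confined to the validation set, although that is the natural reading for the performance of a prediction rule. With all 500 men the missed share roughly halves at a correlation of 0.5 and falls further above it.

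Finally, a fixed ±0.05 margin has no basis in the documents, and two identical laboratories would often fail it. That stands against prescribing the margin, but not against reporting an interval.

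**Conclusion.** The point holds for the AUC component of inferential reproducibility. A test of no difference is the only formal tool there, and by itself it cannot answer the question the objective asks. The planned companions lack acceptance limits, and no interval for the AUC difference is specified.

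The practical size runs from serious to negligible with the unknown correlation: about 59% down to 4% of 0.05 losses missed at 75/175, and about 31% down to under 1% at 150/350. Near 0.9, missed losses largely disappear, but trivial differences start to reach significance, so the p-value remains the wrong summary across the range. The documents do not show that the sponsor intends to read non-significance as agreement; the fault is that nothing prevents it. The objective is secondary, and the main prediction rules come from MSKCC alone, so the primary aims are not affected.

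**What to change.** Add one paragraph to Section 11.0:

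1. For laboratories, time points and platforms, the main summary is the paired AUC difference with its confidence interval by the DeLong method. That method is already reference 20, cited there for the comparison of racial groups. Any p-value is supplementary.
2. A non-significant difference will not be interpreted as agreement.
3. State which patients (validation set or all) and which of the three runs enter the between-laboratory comparison.
4. If the sponsor wishes to claim between-laboratory agreement, it does so only when the interval lies inside a margin that it justifies and fixes before analysis; otherwise the report says that agreement was not shown. For LC-MS, with its 50/50 test set, report the interval only.

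This needs no new samples or assays. The cost is that agreement becomes harder to claim: with equal laboratories and an illustrative margin of 0.05, it would be shown about 19%, 53%, 77% and 97% of the time at 75/175 across the four correlations. Items 1 to 3 alone remove most of the risk of misreading, even if no margin is set.

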12.0 RESEARCH PARTICIPANT REGISTRATION AND RANDOMIZATION PROCEDURES

12.1 Research Participant Registration

Confirm eligibility as defined in the section entitled Criteria for Patient/Subject Eligibility.

Obtain informed consent, by following procedures defined in section entitled Informed Consent Procedures.

During the registration process registering individuals will be required to complete a protocol specific Eligibility Checklist.

All participants must be registered through the Protocol Participant Registration (PPR) Office at Memorial Sloan-Kettering Cancer Center. PPR is available Monday through Friday from 8:30am – 5:30pm at [contact]. The PPR fax numbers are [contact] and [contact]. Registrations can be phoned in or faxed. The completed signature page of the written consent/verbal script and a completed Eligibility Checklist must be faxed to PPR.

12.2 For Participating Sites:

Central registration for this study will take place at Memorial Sloan Kettering Cancer Center (MSKCC).

To complete registration and enroll a participant from another institution, the study staff at that site must contact the designated research staff at MSKCC to notify him/her of the participant registration. The site staff then needs to fax registration/eligibility document to the Department of Surgery/Urology Service at MSKCC [contact].

The following documents must be sent for each enrollment **within 24 hours of the informed consent form being signed:**

- The completed MSKCC eligibility checklist
- The signed informed consent and HIPPA authorization form
- Supporting source documentation for eligibility questions (laboratory results,

**IRB
PB**

Amended: 2/1/12

Memorial Sloan-Kettering Cancer Center IRB Protocol

IRB#: 08-114 A(4)

pathology report, radiology reports, MD notes, physical exam sheets, medical history, prior treatment records and EKG report).

Upon receipt, the research staff at MSKCC will conduct an interim review of all documents. If the eligibility checklist is not complete, the patient be registered PENDING and the site is responsible for sending a completed form within 30 days of the consent.

If the eligibility checklist is complete, participant meets all criteria, all source documentation is received, the participating site IRB has granted approval for the protocol, and the site is in good standing with MSKCC, the MSKCC research staff will send the completed registration documents to the MSKCC Protocol Participant Registration (PPR) Office to be enrolled as stated in section 12.1. The participant will be registered.

Once eligibility has been established and the participant is registered, the participant will be assigned an MSKCC Clinical Research Database (CRDB) number (protocol participant number). This number is unique to the participant and must be written on all data and correspondence for the participant. This protocol participant number will be relayed back to study staff at the registering site via e-mail and will serve as the enrollment confirmation.

13.0 DATA MANAGEMENT ISSUES

A Research Study Assistant (RSA) will be assigned to the study. The responsibilities of the RSA include project compliance, data collection, abstraction and entry, data reporting, regulatory monitoring, problem resolution and prioritization, and coordinate the activities of the protocol study team.

The data collected for this study will be entered into a secure database. Source documentation will be available to support the computerized patient record. Minimal data set will be entered into CRDB.

Participating sites will store specimens until needed for analysis.

13.0.1 Data Management Requirements for Participating Sites

Data and Source Documentation

Data:

Blank data collection tools will be sent to the study staff at each participating site for use. The participating Site PI is responsible for ensuring these forms are completed accurately, legibly and in a timely manner. MSKCC will maintain the central database for data collection.

Participating sites are responsible for maintaining screening and study match lists.

Source Documentation:

**IRB
PB**

Amended: 2/1/12

Memorial Sloan-Kettering Cancer Center IRB Protocol

IRB#: 08-114 A(4)

Source documentation refers to original records of observations, clinical findings and evaluations that are subsequently recorded as data collection tools. Relevant source documentation to be submitted throughout the study, if applicable, includes:

- Diagnosis
- Patient history/MD notes
- Transcripts

13.0.2 Data and Source Documentation Submission

Participating sites should e-mail completed data collection tools files and source documentation to the MSKCC contact provided below. Submissions should include a cover page listing all documents enclosed per participant.

EMAIL: [name] at [contact] and [name] at [contact]

13.0.3 Data and Source Documentation Submission Timelines:

	Baseline	Follow up Visit(s)
Source Documentation	Within 24 hours	14 days from visit date

Data collection tools and source documentation (if applicable) to support data should be submitted to MSKCC on a monthly basis according to chart 1:

Chart I: Sata and Source Documentation Submission Requirements and Timelines

**IRB
PB**

Amended: 2/1/12

Memorial Sloan-Kettering Cancer Center IRB Protocol

IRB#: 08-114 A(4)

	(see section 13.1.1)	
CRFs	Within 7 days of visit	
Eligibility Form	X	
Follow-up Evaluation		X*
Biopsy Evaluation	X	X*
Treatment Evaluation		X*
Prostatectomy Details		X*
Prostatectomy Pathology		X*
New Cancer Evaluation		X*
Survival Status		X *
*if form is applicable according to Follow-up CRF		

